9.1. Statistical Hypotheses

Formal statistical hypothesis testing is not planned. Therefore, adjustments for multiple testing do not apply.

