9.4.2.2. Pharmacokinetic Statistical Inference

Pharmacokinetic parameters will be evaluated to estimate ramucirumab AUC and C_{max} dose proportionality following SC administration in the dose range investigated. Log-transformed ramucirumab C_{max} and AUC parameters will be evaluated in a linear mixed-effects model with fixed effects for dose (Groups 1, 4, and 5 who received 350 mg will be combined). The treatment differences will be back-transformed to present the ratios of geometric means and the corresponding 90% confidence interval (CI).

For ramucirumab SC dosing PK parameters, the t_{max} will be analyzed using a Wilcoxon rank-sum test. Estimates of the median difference based on the observed medians, 90% CIs, and p-values from the Wilcoxon test will be calculated.

Ramucirumab bioavailability will be estimated (see Section 9.4.2.1).

Comparison of AUC and C_{max} between Group 1 and Group 4 will enable to assess the effect of changing the drug product concentration on the exposure. The log-transformed C_{max} and AUC will be the response variable, and the drug product concentration (that is, Group 1 and Group 4) is the explanatory variable.

Comparison of AUC and C_{max} between Group 1 and Group 5 will enable to assess the effect of changing the volume injected at one site of injection on the exposure. The log-transformed C_{max} and AUC will be the response variable, and the volume injected (that is, Group 1 and Group 5) is the explanatory variable.

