## 7. SAMPLE SIZE JUSTIFICATION

Approximately 60 participants will be enrolled and randomly assigned to study intervention (10 per group/dose level; 7 ramucirumab:3 placebo) to obtain at least 48 evaluable participants overall for an estimated total of at least 8 evaluable participants per intervention group (6 ramucirumab and at least 2 placebo). The sample size is not powered on the basis of statistical hypothesis testing. A participant will be considered evaluable when the participant completes up to 40 days of study procedures. When a participant does not complete up to 40 days of study procedures, the sponsor will be consulted if the participant will need to be replaced.

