### 9.3.2 Pharmacokinetic Statistical Methodology

Ramucirumab bioavailability will be estimated. PK parameters will be evaluated to estimate ramucirumab  $AUC_{(0-\infty)}$  and  $C_{max}$  dose proportionality following SC administration in the dose range investigated. Log-transformed ramucirumab  $C_{max}$  and  $AUC_{(0-\infty)}$  parameters will be evaluated in a linear mixed effects model with fixed effects for dose (Groups 1, 4, and 5 who received 350 mg will be combined if appropriate). The treatment differences will be back-transformed to present the ratios of geometric means and the corresponding 90% confidence interval.

For ramucirumab SC dosing PK parameters, the  $t_{max}$  will be analyzed using a Wilcoxon rank-sum test. Estimates of the median difference based on the observed medians, 90% CIs, and p-values from the Wilcoxon test will be calculated to assess similarity or not in  $t_{max}$  between dose level groups 1, 4, 5 combined compared to group 2 and group 6.

The above-mentioned analysis investigating the relationship (e.g. linearity/proportionality) between ramucirumab PK parameters and dose may be adjusted/repeated in the event of significant difference in PK between the 350 mg SC groups (Group 1, 4, 5). Such difference would indicate significant impact of either injection volume or drug product concentration on the PK. In this scenario, the analysis, investigating the relationship (e.g. linearity/proportionality) between ramucirumab PK parameters and dose, may be repeated by excluding the data from one or two of the 350 mg SC group.

Comparison of  $AUC_{(0-\infty)}$ ,  $C_{max}$  and  $t_{max}$  between Group 1 and Group 4 will enable to assess the effect of changing the drug product concentration on the exposure. The log-transformed  $AUC_{(0-\infty)}$ ,  $C_{max}$  and  $t_{max}$  will be the response variable, and the drug product concentration (that is, Group 1 and Group 4) is the explanatory variable.

Comparison of  $AUC_{(0-\infty)}$ ,  $C_{max}$  and  $t_{max}$  between Group 1 and Group 5 will enable to assess the effect of changing the volume injected at one site of injection on the exposure. The log-transformed  $AUC_{(0-\infty)}$ ,  $C_{max}$  and  $t_{max}$  will be the response variable, and the volume injected (that is, Group 1 and Group 5) is the explanatory variable.

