#### Example SAS Code:

```
proc mixed data=data alpha=0.1;
by parameter;
class dose;
model logpk = dose / ddfm=kr residual cl;
lsmeans dose / pdiff=control('1') alpha=0.1;
ods output lsmeans=lsm;
ods output diffs=diff;
run;
```

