### **11. CHANGES FROM THE PROTOCOL SPECIFIED STATISTICAL ANALYSES**

There were no changes from the protocol specified statistical analyses.

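### SAP 9.3.2 makes pooling of the three 350-mg SC groups depend on an undefined significance check, and does not require a matched 700/350 ratio beside the pooled one

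*SAP*

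**What the plan says.** Protocol 9.4.2.2 models log AUC and log Cmax with dose as a fixed effect and reports geometric mean ratios with 90% intervals. Its pooling rule has no condition: "Groups 1, 4, and 5 who received 350 mg will be combined".

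SAP 9.3.2 keeps the model but qualifies the rule: "Groups 1, 4, and 5 who received 350 mg will be combined if appropriate". It then allows the dose analysis to be adjusted or repeated "in the event of significant difference in PK between the 350 mg SC groups (Group 1, 4, 5", and adds that it "may be repeated by excluding the data from one or two of the 350 mg SC group". No test, significance level, PK parameter, size of difference or rule for choosing the excluded group is given.

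Protocol 9.1 states "Formal statistical hypothesis testing is not planned". Protocol 9.4 requires changes in analysis method, with their justification, to be described in the SAP and the study report. SAP 3 says substantial differences will be identified. SAP 11 reads "There were no changes from the protocol specified statistical analyses".

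SAP 9.3.2 also plans, without condition, comparisons of AUC, Cmax and tmax for Group 1 v Group 4 and Group 1 v Group 5. SAP 6 lists the three 350-mg presentations as separate treatments.

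**The concern.** The 700/350 ratio needs a 350-mg reference, and the SAP lets the data influence which groups form it. Groups 4 and 5 exist because concentration and volume per site might change exposure. If they do, pooling puts that effect into the dose contrast.

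The check that is meant to catch this has no defined level and compares about 7 participants with 7. It can fail in two ways:

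- A non-significant result leaves the presentation effect in the ratio.
- A significant result may change the reference after the data have been seen, with no rule for how.

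At stake are the reported dose-proportionality estimate and the meaning of its 90% interval. Both will be read when later SC dosing is planned.

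**Working it through.** **The plan's own figures.** Six groups of 10 give 60 enrolled, and six groups of 8 evaluable give 48; both match SAP 7. No power is stated for the check between 350-mg groups, so there is none to reproduce.

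**Inputs**
- Active participants per group: 7, from "10 per group/dose level; 7 ramucirumab:3 placebo" (SAP 7). At least 6 are to be evaluable.
- Level: none is stated. The nearest is the 90% interval level in the example code, "proc mixed data=data alpha=0.1". I use 0.10 two-sided as an assumption.
- Between-participant log-SD: none is stated. I derive it from the 5th–95th percentiles simulated for SC dosing in Protocol Appendix 6, as ln(P95/P5)/(2 × 1.645). Week-1 AUC: ln(25.1/10.6)/3.29 = 0.26. Steady-state AUC: ln(102/33)/3.29 = 0.34. These come from a patient model, so they are an assumption here.
- Presentation effect: none is stated. I assume 25% above Group 1, in one or both of Groups 4 and 5.

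**Bias of the pooled ratio.** With equal group sizes the pooled reference is the geometric mean of the three groups.
- Both groups shifted: 1.25^(2/3) = 1.160, so a true 2.00 is estimated as 2.00/1.160 = 1.72.
- One group shifted: 1.25^(1/3) = 1.077, so 2.00/1.077 = 1.86.

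**Power of one pairwise check.** Two-sample t-test on log AUC, 12 df, critical value 1.782, noncentrality ln(1.25)/(SD × √(2/7)).
- SD 0.26: 0.2231/(0.26 × 0.5345) = 1.61, power 45%.
- SD 0.34: 0.2231/(0.34 × 0.5345) = 1.23, power 32%.

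**Both checks together.** Simulated trials (100,000 per row), 7 per group, alpha 0.10, true 700/350 ratio 2.00. The last two columns refer to trials in which neither check is significant.

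| Groups shifted 25% | Log-SD | Neither check significant | Mean pooled ratio | 90% CI coverage |
|---|---|---|---|---|
| 4 and 5 | 0.26 | 39% | 1.72 | 66% |
| 4 and 5 | 0.34 | 54% | 1.72 | 76% |
| One only | 0.26 | 50% | 1.86 | 85% |
| One only | 0.34 | 63% | 1.86 | 87% |
| None | 0.26 or 0.34 | about 83% | 2.00 | 90% |

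With no presentation effect, at least one check is therefore significant in about 17% of trials, which could prompt a needless exclusion.

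The check does not create the bias; it fails to remove it. If the groups are pooled in every trial, as the protocol says, the mean ratio with both groups shifted is still 1.72, and coverage is only one to two percentage points higher than in the table. Group 2 v Group 1, reported in every trial, averages 2.00 with 90% coverage in all these scenarios.

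**Precision of the matched contrast.** The standard-error ratio, matched to pooled, is √(2/7)/√(1/21 + 1/7) = 1.22.

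**The case against.** Much of the case on the other side stands.

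- **A reader might infer that a presentation effect would go unseen.** The documents do not support that. Group 1 v 4 and 1 v 5 are compared whatever the result, and SAP 9.1 provides geometric means for AUC and Cmax. A reader could form the Group 2/Group 1 point ratio by hand. Protocol 9.4.2.1 also plans a mixed-effects model with a covariate search. Only the matched ratio with its interval is missing.
- **A reader might infer that the check usually misses a 25% effect.** That is not general. With both groups shifted, 7 per group and alpha 0.10, it misses in about 22% of trials at log-SD 0.20 and 39% at 0.26. Misses exceed half at 0.34 (54%), or at alpha 0.05 (54% and 68% at log-SDs 0.26 and 0.34). Checking Cmax as well adds chances to trigger.
- **A reader might infer that the pooled result would be withheld.** The SAP allows a repeat, which can mean an added run. But it also allows adjustment, and the *if appropriate* qualifier applies to the main analysis, so the text does not settle this.
- **Group 1 is not a perfect match.** Group 2 uses 175 mg/mL, 2 mL per site and two sites. Group 1 differs in number of sites, Group 4 in concentration and Group 5 in volume per site. Group 1 is the natural reference because it shares both factors that Groups 4 and 5 were set up to vary.
- **Opposite effects in Groups 4 and 5 largely cancel.** Ratios of 0.70 and 1.30 to Group 1 bias the pooled ratio by only about 3%.

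None of this defines the trigger or reconciles SAP 11 with the protocol.

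**Conclusion.** The point holds as a question of specification. Pooling is conditional in the SAP and unconditional in the protocol, the condition is undefined, and SAP 11 does not record the difference.

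The size depends on assumed effects and SDs. If both groups are 25% above Group 1, the check stays silent in roughly two to five trials in ten, and the pooled ratio is then about 14% too low (1.72/2.00 = 0.86), with clear under-coverage. If only one group is shifted, the ratio is about 7% too low (1.86/2.00 = 0.93) and the loss of coverage is modest.

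It would be wrong to infer that a trial conclusion is at risk. No hypothesis, proportionality margin or decision rule rests on this ratio. The consequence is limited to the reported estimate and its interval.

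**What to change.** In SAP 9.3.2, delete *if appropriate* and the paragraph that ties exclusion of groups to a significance finding. State instead that two 700/350 ratios for AUC and Cmax, each with a 90% interval, will always be reported side by side:

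1. Group 2 v Groups 1, 4 and 5 pooled, from the protocol's dose model, as the main result.
2. Group 2 v Group 1, from the same form of model with group in place of dose, as a prespecified sensitivity analysis. Describe it as sharing concentration and volume per site and differing in number of sites.

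State that no group is excluded because of a test, and list the added contrast in SAP 11.

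The cost is one extra contrast and no new data. The matched interval is about 22% wider on the log scale, but the pooled one stays beside it. The pooled ratio still carries any presentation effect; the matched ratio is what lets a reader see how much.

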#### Example SAS Code:

```
proc mixed data=data alpha=0.1;
by parameter;
class dose;
model logpk = dose / ddfm=kr residual cl;
lsmeans dose / pdiff=control('1') alpha=0.1;
ods output lsmeans=lsm;
ods output diffs=diff;
run;
```

## **9.4 Safety and Tolerability Assessments**

### **9.4.1 Adverse events**

Where changes in severity are recorded in the Case Report Form (CRF), each separate severity of the AE will be reported in the listings, only the most severe will be used in the summary tables. A pre-existing condition is defined as an AE that starts before the participant has provided written informed consent and is ongoing at consent. A non-treatment emergent AE is defined as an AE which starts after informed consent but prior to dosing. A TEAE is defined as an AE which occurs postdose or which is present prior to dosing and becomes more severe postdose. For Group 6 with SC infusion, the onset time of the AE will be relative to the start of infusion.

All AEs will be listed. TEAEs will be summarized by treatment, group, dose level, severity and relationship to the study drug. The frequency (the number of AEs, the number of participants experiencing an AE and the percentage of participants experiencing an AE) of TEAEs will be summarized by treatment, group, dose level, Medical Dictionary for Regulatory Activities (MedDRA) version 23.0 system organ class and preferred term. The summary and frequency AE tables will be presented for all causalities and those considered related to the study drug by the investigator. CTCAE version 5.0 will be used to assign AE severity grades. Any SAEs will be listed.

Discontinuations due to AEs will be listed.

### **9.4.2 Concomitant medication**

Concomitant medication will be coded using the World Health Organization (WHO) drug dictionary (Version March 2020 B3). Concomitant medication will be listed.

### **9.4.3 Clinical laboratory parameters**

All clinical chemistry and hematology data will be summarized by parameter, treatment, group, and dose level, together with changes from baseline, and listed. Urinalysis data will be listed. Additionally, clinical chemistry, hematology and urinalysis data outside the reference ranges will be listed and flagged on individual participant data listings.

Coagulation and thyroid-stimulating hormone data will be listed.

Samples for serum immunoglobulins, and their derived total, will be summarized and listed by parameter and treatment.

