9.4.3. Other Safety Analyses

All safety analyses will be made on the Safety Population. The most current version of the Medical Dictionary for Regulatory Activities (MedDRA) at the time of analysis will be used when reporting AEs by MedDRA terms, and CTCAE version 5.0 will be used to assign AE severity grades.

All relevant hematology and chemistry laboratory values will be graded according to CTCAE version 5.0.

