10.8. Appendix 8: Protocol Amendment History

The Protocol Amendment Summary of Changes Table for the current amendment is located directly before the Table of Contents (TOC).

Amendment(b): 14 July 2020

Overall Rationale for the Amendment:

This amendment addresses feedback from the United States Food and Drug Administration (FDA).

Section # and Name	Description of Change	Brief Rationale
1.3 Schedule of Activities	Indicated that AE grading will be via CTCAE version 5.0	To address FDA feedback
8.2.6 Safety Monitoring	Indicated that safety monitoring will include monitoring and recording of all AEs, including all CTCAE version 5.0 grades and SAEs	To address FDA feedback
8.3 Adverse Events and Serious Adverse Events	Indicated that the investigator will use CTCAE version 5.0 to assign AE severity grades	To address FDA feedback
9.4.3 Other Safety Analyses	Indicated that the most current version of MedDRA will be used to report AEs and that CTCAE version 5.0 will be used to assign AE severity grades. Indicated that all relevant hematology and chemistry laboratory values will be graded according to CTCAE version 5.0.	To address FDA feedback
10.3.3 Recording and Follow-Up of AEs and/or SAEs	Indicated that the investigator will use CTCAE version 5.0 to assign AE severity grades	To address FDA feedback
11 References	Added reference for CTCAE version 5.0	To address FDA feedback
Throughout	Minor editorial and formatting revisions	Minor and therefore have not been summarized

Abbreviations: AE = adverse event; CTCAE = Common Terminology Criteria for Adverse Events; FDA = United States Food and Drug Administration; MedDRA = Medical Dictionary for Regulatory Activities; SAE = serious adverse event.

Amendment(a): 26 June 2020**Overall Rationale for the Amendment:**

Due to the COVID-19-related increased risks, extending the participant's inpatient visits at the clinical research unit would reduce the exposure and risks.

Section # and Name	Description of Change	Brief Rationale
1.1 Synopsis	Modified the enrollment ratio to 10 participants (7 ramucirumab:3 placebo per group) to complete at least 8 participants	To capture that 10 participants per group will be enrolled
1.1 Synopsis	Added language to indicate that replacements may be enrolled	To add flexibility because replacements may be needed to reach the planned number of completers

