### **3. INTRODUCTION**

This SAP has been developed after review of the Clinical Study Protocol (final version dated 15 May 2020), Protocol Amendment (a) (final version dated 26 June 2020), Protocol Amendment (b) (final version dated 14 July 2020), and Protocol Amendment (c) (final version dated 21 October 2020).

This SAP describes the planned analysis of the safety, tolerability and pharmacokinetic (PK) data from this study. A detailed description of the planned TFLs to be presented in the clinical study report (CSR) is provided in the accompanying TFL shell document.

The intent of this document is to provide guidance for the statistical and PK analyses of data. In general, the analyses are based on information from the protocol, unless they have been modified by agreement with Eli Lilly and Company. A limited amount of information concerning this study (e.g., objectives, study design) is given to help the reader's interpretation. When the SAP and TFL shells are agreed upon and finalized, they will serve as the template for this study's CSR.

This SAP supersedes the statistical considerations identified in the protocol; where considerations are substantially different, they will be so identified. If additional analyses are required to supplement the planned analyses described in this SAP, they may be performed and will be identified in the CSR. Any substantial deviations from this SAP will be agreed upon with Eli Lilly and Company and identified in the CSR. Any minor deviations from the TFLs may not be documented in the CSR.

This SAP is written with consideration of the recommendations outlined in the International Conference on Harmonisation (ICH) E9 Guideline entitled Guidance for Industry: Statistical Principles for Clinical Trials and the ICH E3 Guideline entitled Guidance for Industry: Structure and Content of Clinical Study Reports.

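### The SAP reverses the protocol's ECG listing and summary and is silent on CTCAE v5.0 laboratory grading, yet its Section 11 declares no changes

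*SAP*

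**What the plan says.** **Protocol.** Section 9.4.1.2 names laboratory, vital sign and ECG parameters as the safety parameters, to be both listed and descriptively summarized. Section 9.4.3 adds: "All relevant hematology and chemistry laboratory values will be graded according to CTCAE version 5.0". Appendix 8 dates that sentence to Amendment (b), made in response to FDA feedback: "Indicated that all relevant hematology and chemistry laboratory values will be graded according to CTCAE version 5.0". Section 9.4 requires a change of analysis method that does not need an amendment to be described and justified in the SAP and the clinical study report.

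**SAP.** Section 3 says the plan was written after review of all amendments, including (b), and commits to disclosure: "This SAP supersedes the statistical considerations identified in the protocol; where considerations are substantially different, they will be so identified". The laboratory plan in Section 9.4.3 is: "All clinical chemistry and hematology data will be summarized by parameter, treatment, group, and dose level, together with changes from baseline, and listed". Out-of-range values are flagged in listings; urinalysis, coagulation and thyroid-stimulating hormone (TSH) are listed only. CTCAE appears once, in Section 9.4.1: "CTCAE version 5.0 will be used to assign AE severity grades". Section 9.4.5 treats ECGs as safety monitoring only, with no presentation, and sends clinically significant findings to the adverse event record. Section 11 declares no changes from the protocol's analyses.

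**The concern.** Safety is the first primary objective. Asymptomatic transaminase increases in Groups 1 and 2 led to the 350 mg cap (Protocol 4.1, repeated in SAP Section 5), so laboratory severity is central to this study. A reference-range flag shows that a value is out of range but not its grade. If the SAP is followed as written, rises not recorded as adverse events have no planned grading.

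For ECGs, a change not judged clinically significant would not be reported at all. Intervals could not be compared with placebo, although Protocol 4.2 gives interpretation of safety data as the reason for having placebo.

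Section 11 makes both gaps harder to see, because a reader who relies on it would not look for departures.

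**Working it through.** There is no design figure to reproduce. The check is a comparison of text, followed by a count of the data involved.

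**Text comparison**

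| Item | Protocol | SAP | Reading |
|---|---|---|---|
| ECG parameters | 9.4.1.2: listed and summarized | 9.4.5: not presented | Direct contradiction |
| Chemistry and hematology grading | 9.4.3: CTCAE v5.0 | 9.4.3: not mentioned | Silence |
| AE severity by CTCAE v5.0 | 9.4.3 | 9.4.1: carried over | Consistent |
| MedDRA version | 9.4.3: most current at analysis | 9.4.1: fixed at 23.0 | Different rule |
| Urinalysis, coagulation, TSH | 9.4.1.2: laboratory parameters summarized | 9.4.3: listed only | Minor difference |
| Declared changes | 9.4: describe and justify | 11: none | Incorrect |

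Amendment (b) added three commitments to Protocol 9.4.3: AE severity grading, the MedDRA version rule and laboratory grading. The SAP carries over the first, replaces the second with a fixed version and omits the third. SAP 9.1 restricts summary statistics to what the SAP details, so silence on grading means that no grade summary is planned. SAP 9.1 also promises listings of everything databased, which conflicts with 9.4.5 if ECG data are databased.

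**ECG count** (Protocol 1.3 schedule; 10 per group at 7:3, Protocol 9.2)

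- IV participant: screening, Day -1, Day 1 predose, end of infusion, 6 hours after infusion, Day 2 = 6, of which 3 are post-dose.
- SC participant: screening, Day -1, Day 1 predose, Day 2 = 4, of which 1 is post-dose.
- Six groups (1 IV, 5 SC): 10×6 + 50×4 = 260. Post-dose: 10×3 + 50×1 = 80, made up of ramucirumab 7×3 + 35×1 = 56 and placebo 3×3 + 15×1 = 24.
- Without Group 6 (1 IV, 4 SC): 10×6 + 40×4 = 220. Post-dose: 30 + 40 = 70, made up of ramucirumab 21 + 28 = 49 and placebo 9 + 12 = 21.

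**Laboratory count** (Protocol 1.3; Protocol 10.2.1)

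- Chemistry and hematology are each marked 11 times in the schedule. Less screening, that is 10, which matches the 10 clinical laboratory samples in Protocol 10.2.1. Less Day -1, 9 are post-dose.
- 9×60 = 540 post-dose panels with six groups; 9×50 = 450 without Group 6.

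**The case against.** **The laboratory limb is only silence.** The SAP does not say that grading is dropped, its laboratory sentence does carry out Protocol 9.4.1.2, and Protocol 9.4.3 promises grading without promising a table of grades. Grades might also sit in the unseen output shells, since the SAP says: "A detailed description of the planned TFLs to be presented in the clinical study report (CSR) is provided in the accompanying TFL shell document". This stands as a reason to hold the laboratory limb less firmly than the ECG limb. It does not close the gap: the SAP text commits to no grading, and SAP 9.1 keeps summaries to what the SAP itself details.

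**The ECG approach resembles Protocol 8.2.3.** There the investigator interprets ECGs on site, recordings are stored at the site, and clinically significant findings that lead to a diagnosis become adverse events. No passage says that intervals are databased. This makes the cost of an ECG summary uncertain. It does not reconcile SAP 9.4.5 with Protocol 9.4.1.2.

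**The consequence is small.** Chemistry and hematology are summarized with changes from baseline, listed and flagged. Changes judged clinically relevant are recorded as adverse events (Protocol 8.2.4) and graded. Safety reviews run apart from the final tables, and no inferential safety analysis is planned. All of this is fair, and it limits the loss to rises not recorded as adverse events and to ECG changes below clinical significance.

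**The counts measure volume, and some departures are minor.** Only relevant laboratory values are to be graded, so 540 is an upper bound on scope. Coagulation is scheduled once, at baseline. Whether version 23.0 is the most current MedDRA at analysis cannot be told from the documents. Section 3 of the SAP promises to flag only substantial differences. However, Protocol 9.4 sets a lower bar: changes that fall short of an amendment are to be described and justified.

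**Conclusion.** The concern holds. SAP Section 11 is incorrect as written: the ECG reversal is a plain contradiction and is enough on its own. The absence of laboratory grading is an undeclared omission of a protocol commitment made in response to FDA feedback, subject to whatever the output shells contain.

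The size can be stated only as scope: 260 scheduled ECGs with none presented (80 post-dose), and up to 540 post-dose panels under grading the SAP does not mention; or 220 (70) and 450 without Group 6. These figures assume ten participants per group, no replacements and every scheduled assessment done. The documents give no enzyme or ECG values, so no effect on the safety conclusions can be estimated. The point should be corrected; it does not undermine the design.

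**What to change.** 1. **SAP 9.4.3:** add CTCAE v5.0 grading of relevant chemistry and hematology values and report the grades. Worst post-dose grade by treatment is one possible format. If the output shells already contain grades, say so in the SAP.
2. **SAP 9.4.5:** restore the ECG listing and descriptive summary, or declare and justify the omission.
3. **SAP 11:** compare the SAP with Protocol Section 9 in full and replace the statement with a justified list of departures. From the text reviewed, the list should cover:
   - laboratory grading and ECG presentation, if not restored;
   - urinalysis, coagulation and TSH listed but not summarized;
   - the fixed MedDRA version;
   - the mixed-effect PK model of Protocol 9.4.2.1, which the SAP does not carry over, or where it will be reported (Protocol 9.4.5 allows population PK outside the clinical study report);
   - the Entered and Dose Evaluable populations, absent from SAP Section 8, although Protocol Section 9 assigns no analysis to them;
   - conditional pooling of Groups 1, 4 and 5 and the addition of tmax to the Group 1 versus 4 and Group 1 versus 5 comparisons (both minor).

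The cost is SAP wording and a few standard descriptive tables. The laboratory data are already collected. An ECG summary may also need interval data to be entered, if they are held only at the site; declaring and justifying the omission avoids that.
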